#### **5.4.2 Interruption or Discontinuation of Study Dosing and Entry**

If any of the following occur, no further administration of investigational product will take place and no further subjects will be entered into the study:

1. Death in any subject in which the cause of death is related to investigational product
2. Anaphylactic reaction to investigational product in any subject; or
3. Other events that in the judgment of the study team physician are serious enough to warrant immediate review by the DEC

If one of the above-listed events occurs, a prompt review of safety data and the circumstances of the event in question will be conducted by the study team physician and the DEC to determine whether dosing and study entry should be resumed, whether the protocol will be modified, or whether the study will be discontinued permanently. Review and approval by the DEC are required for resumption of the study in the event the study is interrupted because of one of the above-listed events.

#### **5.4.3 Procedures for handling subjects incorrectly initiated on investigational product**

Patients who fail to meet the inclusion/exclusion criteria should not, under any circumstances, be initiated on investigational product.

Where subjects that do not meet the inclusion criteria are enrolled in error or incorrectly started on treatment, or where subjects subsequently fail to meet the study criteria

Date

postinitiation, the investigator should inform the AstraZeneca Study Delivery Team Physician immediately. The AstraZeneca Study Delivery Team Physician is to ensure all such contacts are appropriately documented.

#### **5.4.4 Procedures for withdrawal from study**

A subject that discontinues will always be asked about the reason(s) for discontinuation and the presence of any AEs. The Principal Investigator or Sub-Investigator will perform the best possible observation(s), test(s) and evaluation(s) as well as give appropriate medication and all possible measures for the safety of the subject. They will also immediately inform AstraZeneca of the withdrawal. AEs will be followed up (see Sections 6.4.3 and 6.4.4).

### **5.5 Study timetable and end of study**

Planned duration of the study:

Study period:

Registration period:

There will be an interim data cut-off defined as the earlier of 6 months after the last subject recruited starts investigational product or 3 months after the final subject discontinues investigational product. Data analysis will be performed and a Clinical Study Report written based on this data set.

Any subjects still receiving investigational product at the time of this data cut-off will be able to continue to receive MEDI-573 while deriving clinical benefit. Such subjects will continue to be monitored and all safety assessments performed until the investigational product is discontinued. In addition, these subjects should be followed up for 3 months after the last dose for any new reports of AEs. A Clinical Study Report Addendum may be prepared to summarise the additional safety data collected between the interim data cut-off and the end of the study.

## **6. STUDY PLAN AND COLLECTION OF STUDY VARIABLES**

### **6.1 Study Plan**

A schedule of screening, treatment visit, and follow-up visit procedures is presented in [Table 5](#) (Cohorts 1 and 2) and [Table 9](#) (Cohort 3).

Date

**Table 5 Study plan (Cohorts 1 and 2)**

Assessment	Screen	Cycle 1					Cycle 2 and Beyond			End of Treatment d	Follow-up		Details in
		Day 1	Day 2	Day 3	Day 8	Day 15	Day 1	Day 8	Day 15		30 days after the last dose	3 months after the last dose	
Allowance (days)	- 28 - 1	—	—	—	—	—	±2	±2	±2		+3	±14	
Written Informed Consent	X						X a						Appendix D
Verify Eligibility Criteria	X	X											4.1, 4.2
Medical History	X												6.3
Pregnancy test b	X	X					X				X		6.3.5
WHO Performance Status	X	X					X			X	X	X c	6.3.2
Physical Examination	X	X					X			X	X	X c	6.3.2
Height	X												6.3.2
Weight	X	X					X			X	X		5.1.2
Vital Signs	X	X		X	X	X	X	X	X	X	X		6.3.3
ECG	X	X					X			X	X		6.3.4
Haematology/ Clinical Chemistry	X	X		X	X	X	X	X	X	X	X		6.3.5
Urinalysis	X	X			X	X	X	X	X	X	X		6.3.5
Tumour assessment (CT or MRI Scans)	X						X c			X		X c	6.9.1
Tumour marker	X						X c			X		X c	6.9.2
PK f		X	X	X	X	X	X	X g	X g	X	X		6.5
Anti-MEDI-573 Antibodies		X					X				X	X	6.5.3
Blood Biomarker Analysis		X	X	X	X	X	X	X	X	X	X		6.7

Date

**Table 5 Study plan (Cohorts 1 and 2)**

Assessment	Screen	Cycle 1					Cycle 2 and Beyond			End of Treatment d	Follow-up		Details in
		Day 1	Day 2	Day 3	Day 8	Day 15	Day 1	Day 8	Day 15		30 days after the last dose	3 months after the last dose	
Allowance (days)	- 28 - 1	—	—	—	—	—	±2	±2	±2		+3	±14	
Insulin/GH		X	X	X	X	X	X	X	X	X	X		6.7
Archived Tumour Sample (Optional) h	X												6.7
Tumour Biopsy (Optional) i	X												6.7
MEDI-573 Administration		X			X	X	X	X	X				5
AE Assessment	X	X	X	X	X	X	X	X	X	X	X		6.4
Concomitant Medications	X	X	X	X	X	X	X	X	X	X	X		4.3.1

a Only cycle 2, if subject would like to continue the study.

b All female subjects of child-bearing must be tested. Serum samples will be used at screening only and urine samples will be used at other visits.

c Tumour assessments will be done at odd cycles only and be required before odd treatment starts.

d All possible measures will be performed at end of treatment.

e Subjects who discontinue the study treatment for reasons other than disease progression or initiation of alternative anticancer therapy will undergo Tumour assessment 3 months after the last dose of MEDI-573.

f PK samples will be collected according to [Table 13](#).

g Only cycle 2.

h If an archived tumour sample is available and the subject provides consent for its use; collect and ship per instructions in the Laboratory Manual.

i If the subject provides consent for its use and the samples are collected in a clinical routine at pre- and post (from day 15 to day 21 in cycle 1)- MEDI-573 treatment, the samples will be shipped per instructions in the Laboratory Manual.

Date

**Table 6 Time window for vital signs (body temperature, respiratory rate, blood pressure and pulse) (Cycle 1, Cohorts 1 and 2)**

Time point	Screen	Day 1							Day 3	Day 8	Day 15
		Pre-dose a	15 min post initiation of infusion	30 min post initiation of infusion	45 min post initiation of infusion	End of infusion	30 min post infusion	60 min post infusion			
Allowance	-	-	±5 min	±5 min	±5 min	±5 min	±5 min	±5 min	-	b	b

a Measurement should be done on the day of the first infusion of MEDI-573.

b Measurement should be done at the same time points as Day 1.

**Table 7 Time window for vital signs (body temperature, respiratory rate, blood pressure and pulse) (Cycle 2 and Beyond, Cohorts 1 and 2)**

Time point	Day 1							Day 8	Day 15	End of Treatment	30 days after the last dose
	Pre-dose a	15 min post initiation of infusion	30 min post initiation of infusion	45 min post initiation of infusion	End of infusion	30 min post infusion	60 min post infusion				
Allowance	-	±5 min	±5 min	±5 min	±5 min	±5 min	±5 min	b	b	-	-

a Measurement should be done on the day of the first infusion of MEDI-573.

b Measurement should be done at the same time points as Day 1.

Date

**Table 8 Time window for ECG (Cohorts 1 and 2)**

Time point a	Screen	Cycle 1				Cycle 2 and Beyond	End of Treatment	30 days after the last dose
		Day 1				Day 1		
		Pre-dose	End of infusion	2 h post infusion	6 h post infusion	Pre-dose		
Allowance	-	-	±5 min	±15 min	±15 min	-	-	-

a All ECGs should be done prior to the PK sampling for corresponding time points. Measurement should be done on the day of the first infusion of MEDI-573.

**Table 9 Study plan (Cohort 3)**

Assessment	Screen	Cycle 1				Cycle 2 and Beyond		End of Treatment d	Follow-up		Details in
		Day 1	Day 2	Day 3	Day 8	Day 1	Day 8		30 days after the last dose	3 months after the last dose	
Allowance (days)	- 28 - 1	—	—	—	—	+2	±2		+3	±14	
Written Informed Consent	X					X a					Appendix D
Verify Eligibility Criteria	X	X									4.1, 4.2
Medical History	X										6.3
Pregnancy test b	X	X				X			X		6.3.5
WHO Performance Status	X	X				X		X	X	X e	6.3.2
Physical Examination	X	X				X		X	X	X e	6.3.2
Height	X										6.3.2
Weight	X	X				X		X	X		5.1.2
Vital Signs	X	X		X	X	X	X	X	X		6.3.3
ECG	X	X				X		X	X		6.3.4

Date

**Table 9 Study plan (Cohort 3)**

Assessment	Screen	Cycle 1				Cycle 2 and Beyond		End of Treatment d	Follow-up		Details in
		Day 1	Day 2	Day 3	Day 8	Day 1	Day 8		30 days after the last dose	3 months after the last dose	
Allowance (days)	- 28 - 1	—	—	—	—	+2	±2		+3	±14	
Haematology/ Clinical Chemistry	X	X		X	X	X	X	X	X		6.3.5
Urinalysis	X	X				X		X	X		6.3.5
Tumour assessment (CT or MRI Scans )	X					X c		X		X c	6.9.1
Tumour marker	X					X c		X		X c	6.9.2
PK f		X	X	X	X	X		X	X		6.5
Anti-MEDI-573 Antibodies		X				X			X	X	6.5.3
Blood Biomarker Analysis		X	X	X	X	X		X	X		6.7
Insulin/GH		X	X	X	X	X		X	X		6.7
Archived Tumour Sample (Optional) g	X										6.7
Tumour Biopsy (Optional) h	X										6.7
MEDI-573 Administration		X				X					5
AE Assessment	X	X	X	X	X	X	X	X	X		6.4
Concomitant Medications	X	X	X	X	X	X	X	X	X		4.3.1

a Only cycle 2, if subject would like to continue the study.

b All female subjects of child-bearing must be tested. Serum samples will be used at screening only and urine samples will be used at other visits.

c Tumour assessments will be done at odd cycles only and be required before odd treatment starts.

d All possible measures will be performed at end of treatment.

e Subjects who discontinue the study treatment for reasons other than disease progression or initiation of alternative anticancer therapy will undergo Tumour assessment 3 months after the last dose of MEDI-573.

f PK samples will be collected according to [Table 14](#).

Date

- g If an archived tumour sample is available and the subject provides consent for its use; collect and ship per instructions in the Laboratory Manual.
- h If the subject provides consent for its use and the samples are collected in a clinical routine at pre- and post (from day 15 to day 21 in cycle 1)- MEDI-573 treatment , the samples will be shipped per instructions in the Laboratory Manual.

**Table 10 Time window for vital signs (body temperature, respiratory rate, blood pressure and pulse) (Cycle 1, Cohort 3)**

Time point	Screen	Day 1									Day 3	Day 8
		Pre-dose a	15 min post initiation of infusion	30 min post initiation of infusion	45 min post initiation of infusion	60 min post initiation of infusion	75 min post initiation of infusion	End of infusion	30 min post infusion	60 min post infusion		
Allowance	-	-	±5 min	±5 min	±5 min	±5 min	±5 min	±5 min	±5 min	±5 min	-	-

a Measurement should be done on the day of the first infusion of MEDI-573.

**Table 11 Time window for vital signs (body temperature, respiratory rate, blood pressure and pulse) (Cycle 2 and Beyond, Cohort 3)**

Time point	Day 1									Day 8	End of Treatment	30 days after the last dose
	Pre-dose a	15 min post initiation of infusion	30 min post initiation of infusion	45 min post initiation of infusion	60 min post initiation of infusion	75 min post initiation of infusion	End of infusion	30 min post infusion	60 min post infusion			
Allowance	-	±5 min	±5 min	±5 min	±5 min	±5 min	±5 min	±5 min	±5 min	-	-	-

a Measurement should be done on the day of the first infusion of MEDI-573.

Date

**Table 12 Time window for ECG (Cohort 3)**

Time point a	Screen	Cycle 1				Cycle 2 and Beyond	End of Treatment	30 days after the last dose
		Day 1				Day 1		
		Pre-dose	End of infusion	2 h post infusion	6 h post infusion	Pre-dose		
Allowance	-	-	±5 min	±15 min	±15 min	-	-	-

a All ECGs should be done prior to the PK sampling for corresponding time points. Measurement should be done on the day of the first infusion of MEDI-573.

Date

## **6.2 Recording of data**

Web Based Data Capture (WBDC) will be used for data collection and query handling. The investigator will ensure that data are recorded on the Case Report Forms (CRFs) as specified in the protocol and in accordance with the instructions provided.

The investigator ensures the accuracy, completeness, and timeliness of the data recorded on the CRF and for the provision of answers to data queries according to applicable information.

For details of data and study management see Appendix E of this Clinical Study Protocol.

The Principal Investigators will record data on the observations, tests and assessments specified in the protocol on the electronic CRFs provided by AstraZeneca. These instructions provide guidance for the recording of study data in the CRF including how to change data incorrectly recorded.

## **6.3 Safety procedures**

### **6.3.1 Enrolment and screening**

At enrolment, each potential subject will provide informed consent prior to starting any study specific procedures (see Appendix D of this Clinical Study Protocol for Ethics and Regulatory Requirements).

Each potential subject is assigned a subject identification number (SID). The SID (XXXXXXXXYYY) consists of a 7-digit centre number (XXXXXXX) and a 3-digit serial number (YYY, starting with 001) issued by each study centre in order of informed consent taken. If a subject withdraws from the study, then the SID cannot be reused.

Demographic data and other characteristics will be recorded and will include date of birth, gender, race, alcohol consumption, smoking history and others. A standard medical, medication and surgical history will be obtained with review of the selection criteria with the patient.

Each subject will undergo screening (see [Table 5](#) and [Table 9](#)) during the 28 days prior to the first dose to confirm eligibility (see Sections [4.1](#) and [4.2](#)). Tumour assessments and other clinical data obtained as standard of care prior to consent may be used for the study provided the assessments prior to the first dose of study treatment. However, no invasive or study-specific screening assessments will be performed until consent is obtained.

### **6.3.2 Physical examination**

Physical examinations and Performance status assessment will be performed as described in [Table 5](#) and [Table 9](#). The physical examinations will include assessments of the head, eyes, ears, nose, and throat, respiratory, cardiovascular, GI, musculoskeletal, neurological, psychiatric, dermatological, haematologic/lymphatic, and endocrine systems; and height (at screening only).

Date

Performance status will be assessed according to WHO criteria (Appendix F).

### **6.3.3 Vital signs**

#### **Body temperature, respiratory rate, and blood pressure/pulse**

Supine blood pressure and pulse will be measured after 10 minutes rest. Assessments will be performed at the time points as shown in the study schedule (see [Table 5](#), [Table 6](#), [Table 7](#), [Table 9](#), [Table 10](#) and [Table 11](#)). If axillary temperature is taken, CTCAE grade will be determined using ‘measured values – 0.5°C’.

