**Table 2 Summary of Dose Cohorts**

Dose Cohort	Number of Subjects	MEDI-573 Dose
1	3-6	5.0 mg/kg as a 60-minute IV infusion once every 7 days
2	3-6	15 mg/kg as a 60-minute IV infusion once every 7 days
3	3-6	30 or 45 mg/kg as a 90-minute IV infusion once every 21 days

Subjects will be enrolled to ensure a minimum of 3 and a maximum of 6 evaluable subjects per cohort. Dose escalation will follow the scheme below, according to the following logic:

If no DLT is observed (for definition see Section 5.1.4) in a cohort of 3 evaluable subjects, then dose escalation may occur. Dose increases will be permitted after review of data from a minimum of 3 evaluable subjects has been performed.

If one subject of the 3 evaluable subjects experiences a DLT, then 3 more evaluable subjects will be enrolled to have 6 evaluable subjects. If only one DLT is observed in the complete cohort of 6 evaluable subjects, then dose escalation may occur.

If 2 or more subjects experience a DLT in a group of up to 6 subjects, irrespective of the number of subjects enrolled, the dose will be considered not tolerated and recruitment to the cohort and dose escalation will cease. If the next lower dose level has 3 evaluable subjects, 3 more evaluable subjects will be enrolled to have 6 evaluable subjects.

At the discretion of the sponsor, an intermediate dose may be chosen for dose escalation. Situations that might prompt selection of an intermediate dose include unexpected toxicities that do not meet the definition of DLT or multiple similar toxicities in a cohort that do not meet the definition of a DLT. If an intermediate dose is chosen, subsequent dose escalation will be to the next predetermined dose provided all the criteria for dose escalation in Rules above are met. Further dose escalation will be based on toxicities observed at each dose level,

Date

and may proceed according to the original dosing schedule or may include additional intermediate dosing steps based on accumulated safety data.

There will be no intra-subject dose escalations.

The dose for subsequent cohorts or a decision to stop recruitment will be agreed by the dose escalation committee (DEC) after review of the data from each cohort (see Section **Error! Reference source not found.**).

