#### **5.1.4 Definition of dose-limiting toxicity**

DLT will be graded according to the NCI CTCAE V4.0 and will be assessed from Cycle 1, Day 1 through Cycle 1, Day 21.

A DLT is defined as:

1. Any Grade 3 or higher non-haematologic toxicity that occurs during the DLT assessment period where a cause other than the investigational product cannot be reasonably justified with the following exceptions:
  - Grade <4 high glucose (fasting) with a duration of <24 hours after administration of MEDI-573
  - Grade 3 fever (in the absence of neutropenia) defined as >40.0°C (39.5°C in the axilla) that resolves to normal or baseline within 24 hours of treatment and is not considered an SAE
  - Grade 3 rigors/chills that respond to optimal therapy
  - Any isolated or transient laboratory changes without associated clinical signs or symptoms.
2. Any Grade 3 or higher haematologic toxicity that occurs during the DLT assessment period where a cause other than the investigational product cannot be reasonably justified.

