#### **Variables**

The following variables will be collected in the CRF for each AE:

- AE (verbatim)
- The date when the AE started and stopped
- CTCAE grade
- Whether the AE is serious or not
- Investigator causality rating against the MEDI-573 (yes or no)
- Action taken with regard to MEDI-573
- Outcome

For SAEs additional variables will be collected including treatment given for the event.

Date

It is important to distinguish between serious and severe AEs. Severity is a measure of intensity whereas seriousness is defined by the criteria in Section 6.4.2. An AE of severe intensity need not necessarily be considered serious. For example, nausea that persists for several hours may be considered severe nausea, but not a SAE. On the other hand, a stroke that results in only a limited degree of disability may be considered a mild stroke but would be a SAE.

The grading scales found in the revised NCI CTCAE version 4.0 will be utilised for all events with an assigned CTCAE grading. For those events without assigned CTCAE grades, the recommendation in the CTCAE criteria that converts mild, moderate and severe events into CTCAE grades should be used.

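### Sections 5.1.4 and 6.3.3 convert axillary temperature in opposite directions, so the axillary threshold for Grade 3 fever is 39.5°C in one and 40.5°C in the other

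*Protocol*

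**What the plan says.** Two places in the protocol convert an axillary temperature for grading.

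- Section 6.3.3 (Vital signs), general rule: "If axillary temperature is taken, CTCAE grade will be determined using ‘measured values – 0.5°C".
- Section 5.1.4 (Definition of dose-limiting toxicity), in the list of exceptions: "Grade 3 fever (in the absence of neutropenia) defined as >40.0°C (39.5°C in the axilla"; the parenthesis then closes. The exception covers such a fever if it returns to normal or baseline within 24 hours of treatment and is not a serious adverse event (SAE).

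Both rules feed one scale. For DLTs, 5.1.4 says "DLT will be graded according to the NCI CTCAE V4.0 and will be assessed from Cycle 1, Day 1 through Cycle 1, Day 21". For adverse events generally, 6.4.3 (Variables) says "The grading scales found in the revised NCI CTCAE version 4.0 will be utilised for all events with an assigned CTCAE grading".

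The grade then drives decisions. The first DLT criterion is "Any Grade 3 or higher non-haematologic toxicity that occurs during the DLT assessment period", where no cause other than the product can reasonably be justified. Section 5.1.3 turns the count into a stopping rule: "If 2 or more subjects experience a DLT in a group of up to 6 subjects", the dose is treated as not tolerated, and recruitment to the cohort and escalation cease.

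The other provisions on body temperature (5.1.2 and Tables 6, 7, 10 and 11) deal with when it is measured. None of them reconciles the two conversions or fixes the route of measurement.

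**The concern.** A single axillary reading can receive two different CTCAE grades, depending on which section the investigator has open. The split falls at Grade 3, the boundary at which a non-haematologic event becomes a candidate DLT.

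Cohorts have 3 to 6 evaluable subjects, so one reclassified event can change the action under 5.1.3:

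- 0 of 3 with a DLT allows escalation, while 1 of 3 requires three more evaluable subjects.
- 1 of 6 with a DLT allows escalation, while 2 of 6 stops it.

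Outside the DLT count, grade also matters for the Grade 2 and higher events that the dose escalation committee reviews (5.1.7), for the dosing guidance that applies after Cycle 1 (5.1.8, Tables 3 and 4), and for the adverse event summaries behind the primary safety endpoint. Temperature is scheduled at seven time points on each infusion day in Cohorts 1 and 2 and at nine in Cohort 3, and both sections expressly provide for an axillary reading.

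**Working it through.** **Inputs**

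- Grade 3 fever cut-off: above 40.0°C (5.1.4).
- Axillary equivalent stated for that cut-off: 39.5°C (5.1.4).
- Adjustment to an axillary reading before grading: −0.5°C (6.3.3).

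Assumption: the inequality sign in 5.1.4 carries over to the figure in brackets, so that Grade 3 means an axillary reading above 39.5°C.

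**Step 1. Offset implied by 5.1.4.** Graded temperature minus axillary reading = 40.0 − 39.5 = +0.5°C. So graded temperature = reading + 0.5.

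**Step 2. Offset stated in 6.3.3.** Graded temperature = reading − 0.5.

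**Step 3. Try to reproduce the 39.5°C of 5.1.4 from 6.3.3.** Solve reading − 0.5 = 40.0, which gives a reading of 40.5°C. The stated 39.5°C is not reproduced. It is reproduced only if 0.5°C is added: reading + 0.5 = 40.0 gives 39.5°C.

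**Step 4. Size of the gap.** 40.5 − 39.5 = 1.0°C, which equals the difference of the offsets, 0.5 − (−0.5).

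**Step 5. Readings around the band**

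| Axillary reading (°C) | Graded as, 5.1.4 | Grade 3 or higher? | Graded as, 6.3.3 | Grade 3 or higher? |
|---|---|---|---|---|
| 39.5 | 40.0 | no | 39.0 | no |
| 39.6 | 40.1 | yes | 39.1 | no |
| 40.0 | 40.5 | yes | 39.5 | no |
| 40.5 | 41.0 | yes | 40.0 | no |
| 40.6 | 41.1 | yes | 40.1 | yes |

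Readings above 39.5°C and up to 40.5°C are the ones on which the sections disagree about Grade 3.

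**Step 6. A wording that would make them agree.** With cut-off c, the 5.1.4 rule is reading + 0.5 > c, which is the same as reading > c − 0.5. Subtracting 0.5°C from the cut-off therefore gives 40.0 − 0.5 = 39.5°C, and the gap becomes 0.0°C. Section 6.3.3 uses the same number and the same sign but attaches them to the measured value.

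**Step 7. When the DLT count can change.** All of the following must hold:

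1. The temperature was taken in the axilla and lay above 39.5°C and up to 40.5°C.
2. The fever occurred from Day 1 to Day 21 of Cycle 1.
3. It fell outside the fever exemption: there was neutropenia, or it did not return to normal or baseline within 24 hours of treatment, or it was an SAE.
4. No cause other than the product could reasonably be justified.
5. The event was graded by 6.3.3 and not by the axillary figure in 5.1.4.

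**The case against.** The arithmetic is hard to dispute. The objections concern its reach, and several of them stand.

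- **The specific figure may prevail.** Section 5.1.4 has its own axillary figure, inside the DLT definition, and an investigator or the committee classifying a DLT may simply use it. That is reasonable, but the protocol does not say that it takes precedence. The figure also sits in the description of an exempted event, whereas 6.3.3 is worded as the rule for CTCAE grade in general.
- **The exemption removes many cases.** A fever without neutropenia that resolves within 24 hours of treatment and is not an SAE is not a DLT under either conversion. This stands, and it is why the conditions in step 7 are narrow.
- **Few temperature readings become adverse events by themselves.** Under 6.4.3, deterioration in a scheduled vital sign is reported as an adverse event only if it meets SAE or DLT criteria or leads to discontinuation; accompanying signs or symptoms are reported instead where present. This stands, with one qualification: because meeting the DLT criteria is itself one of the triggers, the choice of conversion can sometimes decide whether the reading is reported at all.
- **The dosing tables allow discretion.** Tables 3 and 4 apply only after Cycle 1, and 5.1.8 permits continuation for some events. This stands.
- **It may be a drafting slip.** Step 6 makes that plausible. It would explain the contradiction but does not remove it, since the sentence refers to the measured value and sites may apply it as written.

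A reader might also infer that 6.3.3 systematically under-grades fever and that its sign is simply wrong. The documents do not support that. They show that the two sections disagree, not which threshold is right, and the rule operates only when the axilla is used, at a frequency that the protocol does not give. Nor do they show any fever already graded under 6.3.3, or a case report form instruction that repeats the rule.

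**Conclusion.** The contradiction is real as the text stands. The two conversions differ by 1.0°C on one CTCAE scale, and axillary readings above 39.5°C and up to 40.5°C are Grade 3 under 5.1.4 and below Grade 3 under 6.3.3. Nothing else in the protocol settles it.

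The practical effect is limited. It arises only with axillary measurement. It alters a DLT count only under the joint conditions in step 7, and otherwise affects the grade of a fever recorded as an adverse event. How often that would happen cannot be estimated from the protocol. In cohorts of 3 to 6, however, one such event would be enough to change an escalation decision.

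The conclusion rests on reading the bracketed 39.5°C as a strict threshold. Reading it as 39.5°C or above adds only that single value to the band. The protocol reproduces no other CTCAE fever cut-off. If the offset implied by 5.1.4 were applied to the others, the same 1.0°C gap would follow, but the protocol does not say that it should be.

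**What to change.** Reconcile 5.1.4 and 6.3.3 so that one axillary conversion is stated and used for all CTCAE fever grading, including DLT assessment. The sponsor should confirm the direction with its clinical team. If the axillary figure in 5.1.4 is what was meant, rewording 6.3.3 to take 0.5°C off the CTCAE cut-off, and not off the reading, makes the sections agree. If 6.3.3 is what was meant, the bracketed figure in 5.1.4 has to change.

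Having one section refer to the other would keep the rule in a single place. Any site grading guidance that carries the same rule should be aligned.

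The cost is one sentence or one figure in the protocol, plus any matching guidance. No new data, assessments or subjects are needed.
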